NCT02536846

Protocol Title: The effects of antipsychotic drugs on brain metabolism in healthy individuals

Protocol Version date: 4/5/21

PRINCIPAL INVESTIGATOR

[name], MD, PhD

[contact]

Schizophrenia & Bipolar Disorder Program

e-mail: [contact]

PROTOCOL TITLE

The effects of antipsychotic drugs on brain metabolism in healthy individuals.

BACKGROUND

Schizophrenia is a complex psychiatric disorder characterized by alterations in brain structure. It remains unclear yet whether some of these alterations may be related to pathophysiology of illness per se, or are the consequence of brain exposure to the effects of psychotropic drugs. In recent years evidence suggests that exposure to the effects of psychotropic drugs may contribute to some structural and other changes in brain. In this study, we aim to evaluate the effects of short-term antipsychotic medication use in healthy subjects on neuroimaging markers. We will also examine effects of antipsychotic exposure on neurocognitive performance.

The primary aim of this study is to investigate antipsychotic drug effects on brain energy metabolism in 30 healthy people by administering olanzapine over 15 days and using 31P MRS imaging at 4 Tesla. Secondary aims include studying the effects of olanzapine on other neuroimaging markers collected using MRI approaches and cognition.

We plan to study the levels of chemicals associated with cellular energy metabolism: kinetics of enzymes involved in cellular energy metabolism in brains of healthy people before and after use of antipsychotic drug olanzapine for 15 days. In addition, we will also collect data on the structure of the gray matter and white matter; resting state functional brain activity; levels of brain chemicals including glutamate and GABA; white matter integrity; and neurocognition. We will collect whole brain data where possible and focus on the medial prefrontal cortex and parietal cortex as two regions of interest whenever whole-brain data collection is not possible due to technical limitations.

RESEARCH DESIGN AND METHODS

Enrollment: The study will enroll up to 30 healthy people with no history of psychiatric illness or family history of psychosis.

There are no restrictions on subject recruitment based on sex, ethnic background or health status other than those mentioned below. Individuals who do not speak English will be excluded.

Inclusion Criteria

1. Age: 21-50 years old.
2. Male or female.

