3. Without psychiatric diagnosis according to a structured psychiatric interview (SCID; First et al 1994).
4. Without history of a psychotic disorder among parents, siblings, or children.

Exclusion Criteria

1. Significant medical or neurological illness.
2. Unstable/active disease or potential contraindications.
3. Body mass index (BMI) greater than or equal to 30.
4. Taking any other medications, including over the counter supplements, with the exception of oral contraceptives for women.
5. Pregnancy. Females of child-bearing age must be using an effective contraceptive method.
6. History of smoking, substance abuse or dependence.
7. Contraindication to MR scan,
8. Medical condition that would prevent blood draws.

This study will be comprised of three main parts. The subject is free to withdraw from the study at any time. Similarly, the investigators may decide to stop the study if the purposes of the study cannot be met. All participants will be asked not to use alcohol or any other substances and drugs during the study period.

1. **Baseline Assessments:** The first part of the study will be carried out within 10 days of study entrance and consists of 3 separate visits which will take about 8 hours in total. This part of the study will consist of the following procedures:
 - a. Consenting procedures (20 minutes)
 - b. Clinical evaluation (120 minutes)
 - c. Urine toxicology screen (5 minutes) and blood pregnancy test (5 minutes)
 - d. MRI procedure:
 - i. Common Anatomic Protocol (CAP) at 3T (MR Scan at 3T – 1) (45 minutes)
 - ii. MRS protocol at 3T (MR Scan at 3T – 2) (30 minutes)
 - iii. Phosphorous MRS/MT at 4T (MR Scan at 4T – 1) (90 minutes)
 - iv. Diffusion Tensor Spectroscopy (DTS) at 4T (MR Scan at 4T – 2) (90 minutes)
 - e. Fasting (12 hours) blood draw of 20 mL (10 minutes)
 - f. Assessment of vital signs, weight, height, waist and hip circumference (5 minutes)
 - g. ECG (10 minutes)
 - h. Neuropsychiatric assessment (60-90 minutes)
 - i. MATRICS Consensus
 - i. 24-Hour food recall (Total Dietary Intake ASA24)
2. **Study Visits:** The second part of the study in which participants will take daily antipsychotic medication will be carried out within 15 days. There will be 5 separate visits on 1st, 2nd, 5th, 10th, and 14th days of medication and each visit will take about thirty to sixty minutes.

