Participants will take daily olanzapine as the antipsychotic medication, Zyprexa Zydis. On the first day of medication each participant will take Zyprexa Zydis 2.5 mg/day PO. Dose will be increased in the second day and participants will be taking Zyprexa Zydis 5 mg/day, PO, for the following days.

The medication will always begin on weekdays except Friday. On the 1st and 2nd day of the medication, participants will be asked to take the medication at McLean Hospital. After they take the medication we will monitor them closely for 1 hour to observe any side effects.

If the participants do not have any unacceptable side effects in the first two days, then they will be able to take the 13 remaining doses at home starting from the third day

On the 2nd, 5th, and 10th days of medication we will administer LUNERS (Liverpool University Neuroleptic Side Effect Rating Scale), ESRS (Extrapyramidal Symptom Rating Scale) and the Columbia Suicide Severity Rating Scale to assess potential side effects better. Weight and vital signs assessment, random blood glucose test will be done and ECG will be taken in these visits. On 5th, 10th, and 14th days all participants will have blood drawn for assessment of olanzapine plasma levels. Each visit will take about 30 minutes to an hour.

Participants' dietary intake will be assessed throughout the study using the 24-Hour Food Recall ASA24 at visits 3 and 8, and with the Food Craving Questionnaire-Trait-reduced (FCQ-T-r) at the 1st, 7th and 9th visits.

We will still complete the study with participants who miss up to 3 days of medication administration and qualify those participants as having received the intended course of medication (while recording their degree of noncompliance). Participants who miss more than 3 days of medication will be discontinued from the study.

3. **Endpoint Assessments:** All participants will undergo final investigations on the 15th and 16th days of the medication follow up period. The participants will take their last olanzapine dose on the evening of the 15th day. They will not be asked to take it on the 16th day as we plan to finish all final assessments during daytime and they take their medications in the evening. Participants will undergo 4T MR scan and neurocognitive testing on the 16th day. All other assessment and 3T MR scans will be done on the 15th day. The third part of the study will consist of the following procedures:
 - a. Clinical evaluation (60 minutes)

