with HIPAA regulations and will store the information securely, protected by web authentication, and Secure Sockets Layer (SSL) encryption. Dietary information captured from the ASA24 is stored in an NIH-designed database that is completely deidentified. The only document linking the participant's username and study number will be kept in a password-protected computer file in a locked office at McLean.

Statistical Analysis: There is no published literature on the effects of olanzapine on the brain measures we plan to study. Therefore, it is not possible to calculate a sample size that would detect a given between-group difference in this study. In fact, our hypothesis is that olanzapine administration does not cause significant abnormalities in brain metabolism. Therefore, we plan to recruit a sample that is large enough to establish the absence of a moderate or large effect. Our proposed sample size of 30 subjects will allow us to detect a difference with effect sizes of 0.45 or greater as significant at the $p<0.05$ level with 80% power. Note that effect sizes of 0.5 are generally considered moderate and 0.8 considered large. Therefore, a non-statistically significant finding with our sample size will suggest that any effects of olanzapine on brain metabolism are at best small. We will examine deviations induced by the study drug on brain metabolism using paired t-tests for before and after measurements.

FORESEEABLE RISKS AND DISCOMFORTS

In terms of olanzapine treatment, the medication may be unsafe for some people and cause some unwanted side effects (*neurological, gastrointestinal, dermatological, ocular, musculoskeletal, hematologic, endocrine, metabolic, psychiatric*).

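### The detectable effect of 0.45 is stated for 30 pairs while enrolment is capped at 30 with no attrition allowance, so any lost pair puts it out of reach, in a study whose favoured result is non-significance

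*Combined protocol and SAP*

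**What the plan says.** Under RESEARCH DESIGN AND METHODS, Enrollment, the number is a ceiling: "The study will enroll up to 30 healthy people". The Statistical Analysis paragraph then uses that ceiling as the analysed number: "Our proposed sample size of 30 subjects will allow us to detect a difference with effect sizes of 0.45 or greater", at p<0.05 with 80% power, with before and after values compared by paired t-tests. It calls 0.5 moderate and 0.8 large, and says that a non-significant result at this sample size would suggest that any effect is no more than small. The stated expectation is a null result: "our hypothesis is that olanzapine administration does not cause significant abnormalities in brain metabolism".

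The same protocol foresees losses:
- Participants may leave whenever they wish (paragraph after the exclusion criteria).
- "Participants who miss more than 3 days of medication will be discontinued from the study" (item 2, Study Visits). Those who miss up to 3 days are kept and counted as treated.
- A participant may end a scan early (MRI/MRS Scan).
- Payment is arranged for people who do not finish (RECRUITMENT PROCEDURES).
- As to the study as a whole, "the investigators may decide to stop the study if the purposes of the study cannot be met".

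The documents give no expected dropout rate, inflated target, replacement rule, minimum number of completed pairs or handling of missing second scans.

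**The concern.** The number enrolled and the number of completed pairs are different quantities, and the plan uses 30 for both. The primary 31P scan is repeated at 4T on day 16, after the last dose, so anyone who leaves during treatment contributes no primary pair. With enrolment capped at the number in the power statement, there is no slack.

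In most trials lost power works against the sponsor's hypothesis. Here it works for it. Fewer pairs make non-significance more likely when a real effect exists, and non-significance is what the plan would read as evidence of at most a small effect. The plan sets no number of completed pairs below which that reading is withheld.

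**Working it through.** **Inputs.** From Enrollment: at most 30 enrolled. From Statistical Analysis: effect size 0.45, significance level 0.05, power 80%, paired t-test, 0.5 as moderate. Not stated: sidedness, whether 0.45 is in units of the SD of the differences, and the dropout rate. I take the SD of the differences as the unit, show both sidednesses, and let the number of pairs fall from 30 to 24 as an assumed range.

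**Step 1: reproduce the plan's figure at 30 pairs.**
- Normal approximation, d = (z for alpha + z for power)/√n. One-sided: (1.645 + 0.842)/√30 = 2.487/5.477 = 0.454. Two-sided: (1.960 + 0.842)/5.477 = 0.511.
- Exact paired t (noncentral t, df = n − 1, noncentrality d√n). One-sided: 0.465. Two-sided: 0.529.

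The one-sided normal approximation comes closest to 0.45. At d = 0.45 with 30 pairs its power is 79.4%, against 77.7% for one-sided exact t and 66.4% for two-sided exact t. A two-sided exact test matches only if 0.45 is in raw-SD units with a before–after correlation of about 0.64, since 0.45/√(2 × (1 − 0.64)) = 0.45/0.849 = 0.530. The documents state neither condition.

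**Step 2: detectable effect at 80% power as pairs are lost.**

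| Completed pairs | One-sided exact t | Two-sided exact t | One-sided normal |
|---|---|---|---|
| 30 | 0.465 | 0.529 | 0.454 |
| 28 | 0.482 | 0.549 | 0.470 |
| 26 | 0.501 | 0.572 | 0.488 |
| 25 | 0.512 | 0.584 | 0.497 |
| 24 | 0.523 | 0.597 | 0.508 |

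The change per lost pair is (0.523 − 0.465)/6 = 0.010 one-sided and (0.597 − 0.529)/6 = 0.011 two-sided. The plan's own benchmark of 0.5 is passed at 24 pairs on the one-sided normal basis (6 of 30 lost, 20%), at 26 on one-sided exact t (4 of 30, 13%), and already at 30 on two-sided exact t.

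**Step 3: chance of missing a true 0.5 SD effect** (one minus exact-t power, noncentrality 0.5√n).
- 30 pairs: noncentrality 0.5 × 5.477 = 2.739; missed 15% one-sided, 25% two-sided.
- 24 pairs: noncentrality 0.5 × 4.899 = 2.449; missed 23% one-sided, 35% two-sided.

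Six lost pairs therefore add about 8 points (one-sided) or 10 points (two-sided).

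**Step 4: what non-significance leaves open at 30.** The 95% interval has half-width 2.045/√30 = 0.373 SD of the differences. A result just short of two-sided significance has an estimate near 0.373, so its interval reaches about 0.373 + 0.373 = 0.75. Non-significance alone does not exclude a moderate effect even with no losses.

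**The case against.** The strongest case against is that attrition is a side issue. By exact t the quoted 0.45 is not met with all 30 pairs, and choosing two sides rather than one moves the detectable effect by 0.529 − 0.465 = 0.064, about six times what one exit does. Treatment lasts 15 days in healthy volunteers, so losses may be few. This stands as to cause and size: the reading of a null result is weak before anyone leaves. It does not remove the mismatch, because the quoted figure still has no allowance for losses that the protocol itself foresees.

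A reader might infer several stronger things that the documents do not support:
- *One withdrawal removes the basis for concluding that effects are small.* One exit costs about 0.01. On the basis closest to the plan's figure, the detectable effect stays below 0.5 down to 25 pairs.
- *Losing four people takes even the most favourable figure to 0.5.* That is true of one-sided exact t (0.501). The one-sided normal figure at 26 pairs is 0.488.
- *Participants will not be replaced.* The documents are silent; they do not forbid it.
- *The investigators may stop the study at will.* The stop is conditional on the study's purposes not being achievable, although how that is judged is not defined.
- *Every listed exit costs a pair.* The Medication paragraph lets a physician stop the drug but does not say that the endpoint scans are then cancelled.
- *The conclusion is free of any sample size.* The plan ties it to its own sample size, given as 30. The gap is that this means people proposed, with no minimum for pairs completed.

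**Conclusion.** The point holds in limited form. The cap and the number in the power statement are the same 30, so 0.45 at 80% power requires full enrolment and no loss, and any lost pair takes the detectable effect above the quoted figure. The effect is gradual: about 0.01 per pair, reaching 0.523 (one-sided) or 0.597 (two-sided) by exact t at 24 pairs, with the chance of missing a 0.5 SD effect up from 15%/25% to 23%/35%. The direction matters more than the size, because the loss favours the hypothesised result.

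The loss of up to 6 of 30 is an assumption, and the figures take 0.45 in units of the SD of the differences. Attrition should not be presented as the origin of the problem with the null conclusion. It makes worse a weakness already present at 30 pairs.

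**What to change.** In the Statistical Analysis paragraph:
1. State whether the test is one- or two-sided, and that the effect size is in units of the SD of the within-person differences.
2. Restate the detectable effect for completed pairs, with rows for 30, 28, 26 and 24 (the table above supplies them).
3. Replace the sentence that reads non-significance as evidence of at most a small effect. Draw that conclusion only if the confidence interval for the standardised mean change, from the pairs actually completed, lies wholly between −0.5 and 0.5. Otherwise report the estimate and interval without it. Apply the same rule after an early stop, and state the confidence level.

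The third item does most of the work, because the interval widens as pairs are lost and so adjusts the claim to the data obtained.

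**Cost.** No extra participants and no change to conduct. The stated detectable effect becomes slightly less favourable, and the null conclusion becomes harder to reach. With a 95% interval and 30 pairs, the observed change must lie within 0.5 − 0.373 = 0.127 SD of zero. With 24 pairs the half-width is 0.422, so the limit is 0.5 − 0.422 = 0.078. If the true effect is exactly zero, the chance of meeting these limits is about 0.51 (|t| below 0.127 × 5.477 = 0.70 on 29 df) and 0.29 (|t| below 0.078 × 4.899 = 0.38 on 23 df). Both treat the observed SD as the true one and are approximate. The sponsor should know before the data are seen that a firm null conclusion may not be available at this size.

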 - b. Urine toxicology screen (5 minutes) and pregnancy test (5 minutes)
 - c. MRI procedure:
 - i. Common Anatomic Protocol (CAP) at 3T
 - ii. MRS protocol to quantify Glu and GABA at 3T
 - iii. Phosphorous MRS/MT at 4T
 - iv. Diffusion Tensor Spectroscopy (DTS) at 4T
 - d. Fasting (12 hours) blood draw of 20 mL (10 minutes)
 - e. Assessment of vital signs, weight, height, waist, and hip circumference (5 minutes)
 - f. ECG (10 minutes)
 - g. Neuropsychological Assessment (60-90 minutes)
 - i. MATRICS Consensus Cognitive Battery
 - h. 24-Hour food recall (Total Dietary Intake ASA24)

Medication: The half-life of olanzapine is 30 hours and one week would be sufficient to reach steady state. However, we decided to give medication longer than 1 week as we know that drug-induced adaptive changes take time to occur. Up until now, the longest duration of olanzapine use in healthy

volunteers has been 15 days. It is a randomized, PBO controlled, two- treatment (OLZ and PBO), crossover study in which the metabolic effects of olanzapine were investigated. 30 healthy men aged between 18-49 years underwent 10 mg/d olanzapine treatment for 15 days (5 mg/d for 3 days, then 10 mg/d for 12 days) in this study ¹⁵. There are also some other multiple-dose studies in which the participants were given daily olanzapine to investigate metabolic effects up to 15 days ^{16, 17, 18, 19}. None of the participants in these studies had major, severe side effects of olanzapine. Based on these studies we determined the duration of medication as 15 days in this study. We determined the daily olanzapine dosage as 5 mg in this study. We aimed to give healthy subjects only 5 mg/d olanzapine, the lower limit of the optimal dose range (5 mg ± 2.5 mg/d), to mimic the therapeutic effect but also protect the participants from adverse effects of treatment.

To assess the potential side effects of olanzapine, we set up 5 separate visits on the 1st, 2nd, 5th, 10th, 14th days of medication period. A physician will be present to monitor all participants' reactions to the medication and stop the medication if they are affected adversely.

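### LUNERS, ESRS and the Columbia scale are named only for days 2, 5 and 10, so as scheduled they give no change from a pre-drug score and miss symptoms first appearing after day 10

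*Combined protocol and SAP*

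**What the plan says.** The relevant text is in the protocol's Research Design and Methods.

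- **Scales.** Under Study Visits: "On the 2nd, 5th, and 10th days of medication we will administer LUNERS", together with "ESRS (Extrapyramidal Symptom Rating Scale) and the Columbia Suicide Severity Rating Scale to assess potential side effects better". This is the only place where any of the three is named. Weight, vital signs, random glucose and ECG are taken at the same visits.
- **Dosing.** Study Visits: "On the first day of medication each participant will take Zyprexa Zydis 2.5 mg/day PO". Endpoint Assessments: "The participants will take their last olanzapine dose on the evening of the 15th day".
- **Visits on drug.** "There will be 5 separate visits on 1st, 2nd, 5th, 10th, and 14th days of medication". The Medication paragraph gives their purpose: "To assess the potential side effects of olanzapine, we set up 5 separate visits". It adds that a physician will watch for reactions.
- **Baseline and endpoint lists.** Each has a clinical evaluation (120 and 60 minutes) whose content is not stated. Both list weight, vital signs and ECG. Neither names LUNERS, ESRS or the Columbia scale.
- **Analysis.** The Statistical Analysis paragraph plans paired t-tests of brain metabolism before and after drug. It describes no analysis of the scales. No control arm is described.

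**The concern.** With no control arm, a participant's own score before drug is the only reference against which a later score can be read. Healthy people can report general complaints without taking anything. The protocol's own list of olanzapine effects, under Foreseeable Risks and Discomforts, includes several complaints of that kind, such as insomnia, nervousness and dizziness. If the first rating is already on drug, a complaint recorded then may have been present beforehand or may have followed the first dose, and the scale cannot say which.

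The other gap is at the end. The Medication paragraph justifies going beyond one week on the ground that adaptive changes need time to develop. The three scales, one of them for suicidality, have no named rating in the last third of that exposure.

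**Working it through.** The plan states no figure on this point, so there is none to reproduce. The check sets the rating days against the dosing days.

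**1. Calendar, from Baseline Assessments, Study Visits and Endpoint Assessments**

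| Time | Three scales named? | Other safety items named |
|---|---|---|
| Baseline (3 visits) | No | Clinical evaluation (undescribed), weight, vital signs, ECG, fasting blood |
| Day 1 | No | Supervised dose, 1 hour of monitoring |
| Day 2 | Yes | As day 1, plus weight, vital signs, glucose, ECG |
| Days 5 and 10 | Yes | Weight, vital signs, glucose, ECG, plasma level |
| Day 14 | No | Plasma level |
| Days 15 and 16 | No | Clinical evaluation (undescribed), weight, vital signs, ECG, fasting blood |

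**2. Counts**

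- Ratings named before the first dose: 0.
- Dosing days after the last named rating: days 11 to 15, so 5/15 = 33%. Day 15 is also an endpoint day and is counted once here; day 16 has no dose.
- Share of the scheduled dose in that stretch: 5 × 5 mg = 25 mg, out of 2.5 + 14 × 5 = 72.5 mg, so 25/72.5 = 34%.

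**3. Can day 2 stand in for a pre-drug rating?**

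The day-2 rating follows at least the day-1 dose. As an illustration, assume one-compartment accumulation, a 24-hour dosing interval and the 30-hour half-life given in the Medication paragraph.

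- Fraction left after 24 hours: f = 2^(−24/30) = 0.574.
- Amount just before the day-2 dose: 2.5 × f = 1.44 mg.
- Steady-state trough on 5 mg/day: 5f/(1 − f) = 6.75 mg.
- Ratio: 1.44/6.75 = 21%. The same sum gives 85% before the day-5 dose and 99% before the day-10 dose.

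Day 2 is therefore an early on-drug rating. Used as the reference, it would absorb whatever followed the first dose.

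**4. What the three ratings can and cannot show**

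- Can: change from day 2 to day 5 and to day 10, including a symptom absent on day 2 and present later.
- Cannot: change from a drug-free score, or anything that first appears after day 10.

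**The case against.** The strongest reply is that silence in the baseline and endpoint lists proves little, because those lists are not complete. The structured psychiatric interview required by the third inclusion criterion is not itemised at baseline and presumably sits inside the 120-minute clinical evaluation. The food craving questionnaire is assigned to visits 1, 7 and 9. With three baseline and five medication visits numbered in order, visits 1 and 9 are a baseline and an endpoint visit, yet neither list names it. This stands. The documents support saying that no pre-drug rating is named, not that none will be made. Still, where the protocol uses these scales it gives their days, and it gives only three.

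A reader might also infer that the Medication paragraph and Study Visits contradict each other, since five visits are for side effects and only three carry the scales. They do not strictly conflict. The Medication paragraph does not promise the scales at every visit, and Study Visits presents them as an addition. Days 1 and 14 can serve the stated purpose through physician observation.

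Nor is the late period unobserved. There is a day-14 visit, and the endpoint has a clinical evaluation, weight, vital signs, ECG and fasting blood. The gap concerns three scales only.

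Finally, a pre-drug score would not prove causation. In a single-arm study it gives within-person change, which time or repeated rating could also produce. That limits what the added rating can claim, but does not remove its use.

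**Conclusion.** The point holds in a limited form. As scheduled, LUNERS, ESRS and the Columbia scale have no named pre-drug rating and none in the last 5 of 15 dosing days. Change from a drug-free score on these scales cannot be calculated, earlier complaints cannot be separated from early on-drug ones, and late-appearing symptoms fall outside them.

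A reader might go further and conclude that drug-emergent change cannot be measured in this trial. The documents do not support that. Emergence between day 2 and day 10 is captured, and weight, vital signs and ECG have baseline, on-drug and endpoint values.

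The scales are safety monitoring. They are neither a primary nor a stated secondary aim, and the primary imaging comparison is untouched. This is a cheap improvement worth making, not a threat to the main result.

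The conclusion assumes that the undescribed clinical evaluations do not already contain the scales. The 21% figure for day 2 is illustrative; the conclusion needs only that day 2 comes after a dose.

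**What to change.** - If the baseline and endpoint clinical evaluations already include the three scales, say so and name the visits. One sentence closes most of the point.
- If they do not, record LUNERS, ESRS and the Columbia scale once before the first dose, at an existing baseline visit or on day 1 before dosing, and once at an existing visit on day 14 or 15.
- State that within-person change from the pre-drug rating will be summarised descriptively, without attributing it to olanzapine, because there is no control arm.
- State in one place which visits carry the scales.

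This changes measurement only: no dose, stopping rule or treatment rule is affected. The cost is a short amendment and some extra rating time per participant at two visits that already take place.

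### A non-significant t-test is taken to show at most small effects, yet a true 0.5 SD effect would be missed about 25% of the time; the missed-dose rule adds only two to three points

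*Combined protocol and SAP*

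**What the plan says.** The Background section states the aim: "The primary aim of this study is to investigate antipsychotic drug effects on brain energy metabolism in 30 healthy people", measured by 31P MRS at 4 Tesla. The Statistical Analysis section hypothesises that olanzapine causes no significant abnormality. It sizes the trial to rule out moderate or large effects, gives a detectable effect size of 0.45 with 80% power at p<0.05, calls 0.5 moderate, and reads non-significance as showing effects that are small at most. The only method named is the paired t-test.

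Under Study Visits, after two doses under observation, "they will be able to take the 13 remaining doses at home starting from the third day". Those who miss more than three days are discontinued. For those who miss up to three, the team will "qualify those participants as having received the intended course of medication (while recording their degree of noncompliance". Exposure is also sampled: "On 5th, 10th, and 14th days all participants will have blood drawn for assessment of olanzapine plasma levels". Neither the noncompliance record nor the plasma levels is given a role in any analysis.

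On timing, the Endpoint Assessments text puts the primary measure last: "Participants will undergo 4T MR scan and neurocognitive testing on the 16th day". The remaining endpoint procedures, 3T scans included, fall a day earlier, and the same text notes that "they take their medications in the evening". The Medication paragraph says "The half-life of olanzapine is 30 hours and one week would be sufficient to reach steady state".

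**The concern.** Failing to reject zero does not show that an effect is small. The test can fail because the effect is small or because 30 pairs are too few to see a moderate one. The hoped-for conclusion here is absence of effect, so anything that lowers power makes that conclusion easier to reach. In a trial seeking an effect, missed doses work against the hypothesis. Here they work in its favour.

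Two questions follow: how often the planned reading would be wrong with perfect adherence, and how much the missed-dose rule adds. At stake is a published statement that short-term olanzapine has little effect on brain energy metabolism, resting on a result that a moderate effect could also have produced.

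**Working it through.** **The plan's own figure.** Inputs from the Statistical Analysis section: n=30, p<0.05, 80% power, effect size 0.45; sidedness is not stated. A one-sided normal approximation gives (1.645 + 0.842)/√30 = 0.454, which reproduces 0.45. A two-sided paired t-test detects 0.53 with 80% power, and its power at 0.45 is 66%. I take effect size as the mean change divided by the SD of the paired change, and use the two-sided t-test below.

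**Reading non-significance, full adherence.** At a true 0.5 SD, the non-centrality is 0.5 × √30 = 2.739 on 29 df. Power is 75.4%, so about 25% of trials would be non-significant. With a one-sided 5% t-test the figure would be about 15%.

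**Exposure after missed doses.** Inputs: half-life 30 h; 2.5 mg on day 1, 5 mg on days 2-15; evening dosing; 13 home doses (days 3-15); 4T scan in the daytime of day 16. Assumed: immediate absorption, linear kinetics, one common dosing hour, all patterns of misses equally likely. Each dose is weighted by 2^(−24k/30) = 0.574^k, where k is the number of days before day 15. With full adherence the weighted sum is 11.743. Missing day 15 leaves 1 − 5/11.743 = 57%. Missing days 13-15 leaves 1 − (5 + 2.872 + 1.649)/11.743 = 19%.

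| Home doses missed | Patterns | Median level | Mean level | Lowest | Cumulative dose |
|---|---|---|---|---|---|
| 1 | 13 | 98% | 92% | 57% | 67.5/72.5 = 93% |
| 2 | 78 | 92% | 85% | 33% | 62.5/72.5 = 86% |
| 3 | 286 | 83% | 77% | 19% | 57.5/72.5 = 79% |

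**Effect on the test.** Dilution acts through the mean, so use r = 0.769 for three misses. If m of 30 participants miss three doses and response is proportional to exposure, the effect is d = 0.5 × [1 − (m/30)(1 − r)].

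| m (assumed) | d | Power | Non-significant |
|---|---|---|---|
| 0 | 0.500 | 75.4% | 25% |
| 3 | 0.488 | 73.4% | 27% |
| 5 | 0.481 | 72.1% | 28% |
| 10 | 0.462 | 68.6% | 31% |

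Using cumulative dose (r = 0.793) gives 73.6%, 72.4% and 69.3% power for m = 3, 5 and 10. With one miss each (r = 0.923), power is 74.8%, 74.3% and 73.2%.

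**Interval criterion.** The 95% half-width is 2.045/√30 = 0.373 SD, so the interval lies within ±0.5 SD only if the observed change is within 0.5 − 0.373 = 0.127 SD of zero. By simulation:

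| True effect | Interval within ±0.5 SD | Non-significant |
|---|---|---|
| 0.5 SD, full adherence | 2.5% | 25% |
| 0.5 SD, m = 3 | 2.8% | 26-27% |
| 0.5 SD, m = 5 | 3.1% | 28% |
| 0 | 51% | 95% |

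These take the margin in units of the true SD. Scaled by the sample SD, the first entry is about 2.0% (a non-central t on 29 df with non-centrality 2.739, falling within ±0.127 × √30) and the last is still about 51%.

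**Could a rerun in adherent participants show the dilution?** The expected gap between the two sets is 0.5 × (3/30) × 0.231 = 0.012 SD, or 0.019 SD for m = 5. The sampling error of the difference between a subset mean and the full-set mean is √(1/27 − 1/30) = 0.061 SD, or √(1/25 − 1/30) = 0.082 SD. The noise is four to five times the signal.

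**The case against.** The missed-dose rule is stated in advance, capped, and accompanied by a record and three plasma draws. Retaining partial adherers in the primary analysis is a defensible choice. The documents give no miss rate and no exposure-response relation, and the loss of power is small even if 3 to 5 people each miss the maximum allowed. All of this stands.

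A reader might infer that the rule itself drives the trial towards a null result, pointing to the 19% level at the day-16 scan. The documents do not support that. That figure is 1 of 286 three-miss patterns; only 30 of the 286 fall below half the full level. The Medication paragraph, which argues that adaptive changes need time, points if anything to cumulative dose, which falls only to 79%.

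A reader might also want adherence defined by the last three doses before the scan. That window sorts people badly. It excludes someone who missed only day 13 (level 86%, dose 93%), keeps someone who missed days 10-12 (level 85%, dose 79%), and retains 120 of the 286 three-miss patterns.

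The plan does say that non-significance will only suggest small effects, and the interval criterion is costly if olanzapine truly has no effect. Both are fair. But the suggestion is drawn directly from the p-value, and the cost shows how little 30 pairs can establish about absence.

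**Conclusion.** The main fault is the inference from non-significance. At n=30 with a two-sided test, it would label a true 0.5 SD effect as small about 25% of the time with no missed doses at all. The missed-dose rule is a secondary contributor, raising this to about 27-28% if 3 to 5 of 30 miss three doses. The addition rests on an assumed number of partial adherers, equally likely timing of misses and response proportional to exposure. The 25% rests only on the two-sided test and on effect size being in SDs of the paired change. Nothing here shows that the retention rule or the choice of a paired t-test is wrong. The adherence element alone would be an optional improvement in reporting.

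**What to change.** In the Statistical Analysis section, keep the all-completers paired t-test as primary and leave the retention rule as it is. Report the mean change with its 95% confidence interval. State that effects are small at most only if that interval lies within ±0.5 SD of the paired change, the plan's own benchmark for a moderate effect; otherwise report the result as inconclusive on that question. This needs no new data. Its cost is the lower chance of reaching the claim when there is no effect, 51% against 95%.

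As a minor supporting step, record each missed dose by date and tabulate the number and timing of misses with the results. Use plasma levels descriptively: draw times are not stated, and a daytime draw on day 14 cannot reveal missed evening doses on days 14 and 15.

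If a rerun is wanted, define the set by total missed doses (for example, none) and label it descriptive, because it is selected after baseline. It is also less precise: the 95% half-width is 0.40 SD at n=27 and 0.41 SD at n=25, against 0.37 SD at n=30. Draw no conclusion from whether it agrees with the primary result.
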